11.3 Missing Data

Where data is incomplete despite the efforts to ensure continuous high quality data collection and reporting as detailed in section 9 of the protocol, information relating to the corresponding participant will be excluded from relevant analyses. Where either the result of Multiplex PCR testing or blood culture is absent, data relating to the corresponding participant will be excluded from all analyses.

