5. OUTCOME MEASURES

5.1 Primary Outcome Measure

The primary outcome measure is diagnostic accuracy of the multiplex PCR test, expressed as sensitivity, specificity, and positive and negative predictive values, with uncertainty expressed using 95% confidence limits.

In the primary analysis, these will be calculated by using the paired blood culture as the reference standard (i.e. the blood culture that had been taken contemporaneously). True positivity will be defined as the PCR test detecting the same genus of organism as identified in the paired blood culture.

Acknowledging that there is no perfect reference standard for sepsis, a secondary analysis will be undertaken, using a less stringent reference standard to resolve discrepant results in a 'fair umpire' test³⁷. This will be applied when the PCR test is positive and the paired blood culture is negative. In this analysis, true positivity will be defined as either:

- (i) culture of the same genus of organism in blood or other sterile site culture within 7 days of the test sample being taken; or
- (ii) culture of the same genus of organism from a non-sterile anatomic site within 3 days of the test sample being taken which is judged, by the patient's clinical team, to represent a focus of infection.

Furthermore we will undertake analysis of the primary outcome measure when multiplex PCR testing is conducted at the point of care, vs. centrally, using both the paired blood culture and the fair umpire test. The primary outcome (diagnostic accuracy) will be re-analysed including only those samples tested at the point of care and compared to the same metrics obtained when only those samples tested centrally are included.

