9. SCHEDULE OF ASSESSMENTS AND STUDY PROCEDURES

9.1 Schedule of Assessments

All patients will be evaluated during the study and data collected at each of the following time-points. For routinely collected clinical data the NHS record will be the source document and for study specific clinical measurements the CRF will be the source document.

Baseline

- Patient Demographics (date of birth, gender)
- Date and Time of ICU admission
- Suspected Source of Sepsis
- The Acute Physiology and Chronic Health Evaluation score (APACHE II) at ICU admission

At Sampling

- Site, Date and Time of sampling
- Previous Antibiotic regimens within 3 calendar days of sampling (Yes/No)
- Determinants of SOFA Score at time of sampling

Additional Assessments

- Paired blood culture result
- Multiplex PCR result
- Date and Time Multiplex PCR test completed
- Date and Time clinical team informed of blood culture result
- Results of additional blood and other sterile anatomic site cultures taken within +/-7 days of the research blood sample for suspected sepsis will also be recorded.
- Results of cultures from non-sterile anatomic sites within +/-3 days of the research blood sample for suspected sepsis will be recorded. Whether the treating physician judged this to represent a clinically-suspected focus of infection will also be recorded.

At Discharge

- Date of critical care discharge
- Date of hospital discharge

Mortality

- Date of death (within 28 days of recruitment)

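### On its natural reading, the exclusion rule in 11.3 removes samples with incomplete umpire records from the PCR-positive/culture-negative cell alone, which tends to raise fair-umpire specificity and PPV

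*Protocol*

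**What the plan says.** Section 11.3 of the protocol has two rules. The stricter one covers the two core results: "Where either the result of Multiplex PCR testing or blood culture is absent, data relating to the corresponding participant will be excluded from all analyses". For any other incomplete data, "information relating to the corresponding participant will be excluded from relevant analyses". The section points back to the data collection of section 9, so the second rule reaches the items listed in 9.1.

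Section 5.1 sets out a secondary fair-umpire analysis to resolve discrepant results: "This will be applied when the PCR test is positive and the paired blood culture is negative". Such a sample becomes a true positive in one of two ways:
- (i) "culture of the same genus of organism in blood or other sterile site culture within 7 days of the test sample being taken";
- (ii) "culture of the same genus of organism from a non-sterile anatomic site within 3 days of the test sample being taken", if the clinical team judges it a focus of infection.

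Section 9.1 collects the data for these criteria, and not for discordant samples alone: "All patients will be evaluated during the study and data collected at each of the following time-points". The items include cultures from blood and other sterile sites within 7 days either side, non-sterile cultures within 3 days either side, and the judgement: "Whether the treating physician judged this to represent a clinically-suspected focus of infection will also be recorded". Section 6.1 blinds site teams to the PCR result.

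**The concern.** Only a PCR-positive/culture-negative sample needs umpire data to be placed in the umpire 2x2 table. The other three combinations are fixed by the PCR and the paired culture. If *relevant* means that the analysis needs the missing item, a gap in the umpire record removes a PCR-positive/culture-negative sample, while a sample negative on both tests with the same gap stays in. Whether a sample is kept then depends on its index and reference results, which is a form of partial-verification bias.

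At stake are the umpire specificity and PPV, mostly in the direction that favours the test. The umpire and primary tables would also rest on different samples, so the difference between them would mix reclassification with deletion. Section 5.1 uses the umpire standard again in the point-of-care versus central comparison, so the same question arises there.

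**Working it through.** **Inputs from section 11.1:** 4501 samples, 10% positive, sensitivity 90%, specificity 95%. The plan's own sample sizes reproduce with z²p(1−p)/d²:
- overall: 1.96² × 0.9 × 0.1 / 0.03² = 384.2, rounded up to 385; 385/0.10 = 3850 (stated 3851);
- uncommon pathogens: 1.96² × 0.9 × 0.1 / 0.20² = 8.64, rounded up to 9; 9/0.002 = 4500 (stated 4501).

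**Expected cells before the umpire**
- PCR+/culture+: 4501 × 0.10 × 0.90 = 405.1
- PCR−/culture+: 4501 × 0.10 × 0.10 = 45.0
- PCR+/culture−: 4501 × 0.90 × 0.05 = 202.5
- PCR−/culture−: 4501 × 0.90 × 0.95 = 3848.4

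**Assumptions not in the protocol:** *c* is the share of PCR+/culture− samples that the umpire would confirm, and *m* is the share of them with incomplete umpire records. Missingness is taken as random within that cell.

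**Formulas**
- Complete data: PPV = (405.1 + 202.5c)/607.6; specificity = 3848.4/[3848.4 + 202.5(1−c)].
- After deletion from that cell: PPV = [405.1 + 202.5c(1−m)]/[405.1 + 202.5(1−m)]; specificity = 3848.4/[3848.4 + 202.5(1−c)(1−m)].

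**Worked case, c = 40%, m = 20%** (202.5 × 0.2 ≈ 41 samples deleted)
- PPV: 486.1/607.6 = 80.0% becomes 469.9/567.1 = 82.9%, up 2.9 points.
- Specificity: 3848.4/3969.9 = 96.94% becomes 3848.4/3945.6 = 97.54%, up 0.60 points.
- Sensitivity: 486.1/531.1 = 91.5% becomes 469.9/514.9 = 91.3%, down about 0.3 points.
- NPV: 3848.4/3893.4 = 98.84%, unchanged.

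**Range** (change in points, specificity / PPV)

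| Confirmed | 5% missing | 10% missing | 20% missing | 30% missing |
|---|---|---|---|---|
| 20% | +0.19 / +0.9 | +0.39 / +1.8 | +0.78 / +3.8 | +1.18 / +5.9 |
| 40% | +0.15 / +0.7 | +0.30 / +1.4 | +0.60 / +2.9 | +0.90 / +4.4 |
| 60% | +0.10 / +0.5 | +0.20 / +0.9 | +0.41 / +1.9 | +0.61 / +3.0 |

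**Direction without random missingness.** Deletion from this cell can only lower or leave the false-positive count, and the true negatives stay, so specificity cannot fall. PPV rises only if the confirmation rate among the deleted samples is below the complete-data umpire PPV, here 80%. If all 41 would have been confirmed, PPV falls to (486.1 − 40.5)/(607.6 − 40.5) = 78.6% and specificity does not move.

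**Alternative reading.** If the same share is dropped at random from all four cells, every cell shrinks by the same factor and all four measures are unchanged. The cost is lost samples: 20% of 4501 is about 900, nearly all of them classifiable without umpire data.

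**Participant-level removal.** Section 7.4 lets a patient contribute several samples. Removing 0.2 to 0.5 further samples per deleted discordant sample (at c = 30%, m = 10%) leaves specificity at 96.79% and PPV at 78.28%, the same as deleting the discordant samples alone.

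**Bounds if nothing is deleted, c = 40%, m = 20%.** All unresolved counted as not confirmed: PPV = 469.9/607.6 = 77.3%. All counted as confirmed: PPV = (469.9 + 40.5)/607.6 = 84.0%. These bracket the complete-data 80.0%.

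**The case against.** **The text does not say that only discordant samples are dropped.** Section 11.3 names no cell of the table. Section 9.1 records the umpire items for all patients and sites are blinded to PCR, so gaps can occur anywhere. A reader might infer that the protocol prescribes deletion from one cell; it does not. That is the natural reading of *relevant*, but not the only one. This stands. The other reading avoids bias only if gaps are equally common in all cells, and it discards samples whose classification never uses the missing item, while section 11.1 makes no allowance for missing data.

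**PPV need not rise.** A reader might infer that the bias always favours the test. For specificity the direction is settled; for PPV it is not. An unrecorded judgement matters only where a same-genus non-sterile culture already exists and criterion (i) is unmet. Such samples may be confirmable more often than the rest, and PPV could then fall. This also stands.

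**The size rests on assumed rates.** A patient with complete records and no further culture simply fails the umpire criteria and is not missing data. With NHS records as source, data queries and monitoring, gaps may be few. At 40% confirmed, the specificity shift exceeds its 95% half-width of about 0.54 points at 20% missing but not at 5% or 10%, so no general claim that it exceeds sampling error is supported.

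**Section 5.1 might be thought to settle the matter** by making any sample that is not shown to meet the criteria a false positive. It defines confirmation but is silent on unrecorded data, so it neither resolves 11.3 nor clearly contradicts it.

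**This is secondary, and detail can go in the SAP.** The analysis is indeed secondary, and STARD reporting (11.2) would show losses. But 11.3 states an exclusion rule rather than leaving the matter open, so an SAP that follows it inherits the problem.

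**Conclusion.** The concern holds in conditional form. On the natural reading of 11.3, incomplete umpire records delete PCR-positive/culture-negative samples alone from the fair-umpire analysis. Specificity then cannot fall. PPV rises under random missingness within the cell whenever confirmation is below 100%, and sensitivity drops slightly. With 40% confirmed and 5% to 20% missing, both assumed, the shifts are about 0.15 to 0.6 points in specificity and 0.7 to 2.9 points in PPV. On the other reading there is no bias under uniform missingness, but a needless loss of samples. Either way the rule serves the analysis worse than keeping every sample. The primary paired-culture results are unaffected, so this is a worthwhile correction to a secondary analysis and not a threat to the main conclusion.

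**What to change.** In section 11.3, state that no sample with both a PCR and a paired culture result is removed from the fair-umpire analysis because umpire data are incomplete. Report the umpire 2x2 table on the same denominator as the primary analysis, with two bounds:
- all unresolved PCR-positive/culture-negative samples counted as not confirmed, as the conservative headline;
- all of them counted as confirmed.

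State the number unresolved beside the table.

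The cost is one sentence in 11.3 and one extra row of results. The headline has its own downside: it understates PPV by 2.7 points in the 40%/20% example (77.3% against 80.0%), close to the 2.9 points by which deletion overstates it. It should therefore always be read with the upper bound (84.0%). The gain is that the remaining uncertainty is visible and bounded.

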7. PATIENT ELIGIBILITY, SCREENING AND RECRUITMENT

7.1 Eligibility Criteria

Patients will be screened for eligibility based on the inclusion/exclusion criteria outlined below.

7.1.1 Inclusion criteria:

1. Patients with suspected sepsis undergoing blood sampling for culture in the course of routine care.

7.1.2 Exclusion criteria:

1. Patients aged <16 years old.
2. Patients previously recruited to the study.
3. Consent declined.

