7.4 Recruitment

In order to estimate the overall sensitivity of the test 4501 samples are required and will be tested to assess the diagnostic accuracy of the Multiplex PCR test. This will be achievable given the high incidence of suspected sepsis in the critically ill and the large number of patients expected to meet the eligibility criteria. Each patient can contribute more than one sample to this study; however an interval of at least 5-days must lapse between consecutive samples obtained.

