9.2 Study Procedures

9.2.1 Blood Sampling

Blood cultures will be taken in the usual manner, for the participating study site, in the course of routine care. At the time that each blood culture is taken from an eligible patient, a 5ml sample of blood will also be collected for multiplex PCR testing. An additional 10ml sample of blood will also be collected where

- (i) it is the first sample
- (ii) research staff are available to process and store the sample

In patients meeting these criteria, and where resources permit, a further 3ml sample of blood will be taken into RNA preservation reagent (Tempus) tubes.

The research blood will be obtained from the same sampling event as the matched blood culture (i.e. from the same syringe draw); if this is not possible then research blood should be obtained by the same sampling technique (i.e. venepuncture or accessing the same vascular device).

When multiple sampling sites are being used for routine clinical blood cultures at the same time, the peripheral (venepuncture) sample is preferred for matched sampling in this study. If a peripheral sample is not being obtained in routine clinical care, then obtaining matched research and routine culture samples from a vascular access device is acceptable.

At participating sites in England, Wales and Northern Ireland, patients undergoing blood culture in the course of routine clinical care will have a research blood sample taken at the same time. The research blood sample will be stored pending informed consent/assent being obtained within 72 hours of taking the sample. No research blood samples will be tested until consent/assent for participation in this study has been obtained. In the event that consent/assent is not obtained the entire research sample will be discarded with no research tests being carried out on it.

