11. STATISTICAL CONSIDERATIONS

11.1 Sample Size

The sample size is based on:

- (i) an assumed 10% event rate for true positive results among specimens collected – this is based on pilot data collected in a single centre.
- (ii) an estimated overall test sensitivity of 90%, and specificity of 95%.
- (iii) the need to ensure that the overall test sensitivity is estimated with a high degree of precision. We have set this precision as +/-3%, at the 95% confidence level.
- (iv) the ability to assess performance of the test for detecting pathogens for which true positive results are expected as infrequently as 1 in 500 tests. We have set the precision for this as +/-20%, at the 95% confidence level
- (v) Given a 10% event rate for true positive results, a sample size that achieves the proposed degrees of precision for the sensitivity estimate will enable the specificity of the test to be measured with even greater precision.

With an assumed sensitivity of 90% with a 10% true positivity rate, in order to estimate the overall sensitivity of the test with a precision of +/-3% at the 95% confidence level, 3851 samples are required. For uncommon pathogens, with an assumed sensitivity of 90% with a 0.2% true positivity rate, in order to estimate the overall sensitivity of the test with a precision of +/-20% at the 95% confidence level, 4501 samples are required. Therefore, 4501 samples will be tested to assess the diagnostic accuracy of the test using these parameters.

The sample has not been inflated for dropouts or missing data because: (i) research sampling is not necessary after the day of enrolment; (ii) the follow-up period is very short; and (iii) the nature of ICU care presents minimal risk of attrition for follow-up.

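### Section 11.3 excludes the whole participant when one test result is absent, although the sample is the unit of analysis; failed PCR runs leave the estimates, and 11.1 gives no reason that covers this loss

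*Protocol*

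**What the plan says.** Section 11.3 has two rules. For incomplete data in general, the participant's information is left out of the analyses it bears on. For an absent test result the rule is wider: where "either the result of Multiplex PCR testing or blood culture is absent, data relating to the corresponding participant will be excluded from all analyses".

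The rest of the design counts samples. Section 11.1 sets 4501 samples, with event rates per specimen, and section 5.1 compares each PCR result with its own paired blood culture. Section 7.4 states: "Each patient can contribute more than one sample to this study; however an interval of at least 5-days must lapse between consecutive samples obtained". Section 9.2.1 agrees, because it takes the additional 10 ml of blood only where "it is the first sample".

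Section 11.1 says "The sample has not been inflated for dropouts or missing data because" and gives three reasons: no need for research sampling beyond the enrolment day, a short follow-up, and little attrition in ICU.

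Section 11.2 commits to STARD reporting, with an account of lost participants.

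**The concern.** Exclusion by participant does not fit an analysis of samples. If a patient gives three samples and one PCR run yields nothing, two complete pairs are discarded as well. Each further sample is another chance to trigger removal. Because samples must be at least 5 days apart, repeat samples come from patients who stay longer, so the loss is not spread evenly over patients.

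The scope is also too wide. An absent PCR result removes the patient from time to result and from costing, not only from accuracy. The time to result of a blood culture does not need a PCR result, and a failed run still uses staff time and disposables. Accuracy is then estimated only among samples for which the device produced an answer.

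The rule leaves a case open where it matters. Under section 9.2.2.1 the later samples are tested at the bedside and again centrally. Section 11.3 does not say whether a failed bedside run with a valid central result counts as absent, yet section 5.1 plans to compare the two settings.

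Finally, none of the reasons in 11.1 deals with a missing PCR or culture result, which is the one event that triggers exclusion from everything.

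**Working it through.** **Inputs from section 11.1:** sensitivity 90%; event rates 10% overall and 0.2% for uncommon pathogens; target half-widths of 3 and 20 percentage points at 95% confidence; stated sizes 3851 and 4501; no inflation.

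**Inputs not in the protocol (assumed):** per-sample rate f of absent results, independent between samples; number of samples per patient.

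**1. The plan's own figures.** Cases needed = 1.96² × 0.9 × 0.1 / d², rounded up, then divided by the event rate.
- Overall: 384.15 → 385; 385 / 0.10 = 3850 (stated 3851).
- Uncommon: 8.64 → 9; 9 / 0.002 = 4500 (stated 4501).

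Both reproduce to within one sample.

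**2. Tolerance to loss.**
- Overall target: 1 − 3851/4501 = 14.4%.
- Uncommon-pathogen target, without rounding cases up: 8.643 / 0.002 = 4322 samples; 1 − 4322/4501 = 4.0%.

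Half-width = 1.96 × √(0.09 / cases), with cases = 4501 × (1 − loss) × event rate:

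| Loss of samples | Samples left | Overall half-width (points) | Uncommon-pathogen half-width (points) |
|---|---|---|---|
| 0% | 4501 | 2.77 | 19.60 |
| 5% | 4276 | 2.84 | 20.11 |
| 10% | 4051 | 2.92 | 20.66 |
| 15% | 3826 | 3.01 | 21.26 |

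**3. Participant-level against sample-level exclusion.** A patient with m samples is removed with probability 1 − (1 − f)^m. At f = 5% this is 5.0%, 9.75% and 14.3% for m = 1, 2, 3. The share of all samples lost is 1 − Σ w·m·(1 − f)^m / Σ w·m, where w is the share of patients giving m samples.
- One sample per patient, f = 5%: 5.0%, so no extra loss.
- 80/20% giving 1/2 samples, f = 5%: 1 − (0.8 × 0.95 + 0.4 × 0.9025)/1.2 = 1 − 1.121/1.2 = 6.6%.
- 70/20/10% giving 1/2/3 samples, f = 5%: 1 − (0.7 × 0.95 + 0.4 × 0.9025 + 0.3 × 0.8574)/1.4 = 1 − 1.2832/1.4 = 8.3%.
- The same 70/20/10% split, f = 10%: 1 − (0.63 + 0.324 + 0.2187)/1.4 = 16.2%, against 10% by sample.

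**4. Failed runs and the estimates.** If sensitivity is 90% among completed runs and failed runs in culture-positive samples count as non-detections, sensitivity is 0.90 × (1 − f): 88.2%, 85.5% and 81.0% at f = 2%, 5% and 10%. Under 11.3 this difference does not enter the estimate.

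**The case against.** **The numerical effect may be small.** This stands. Repeat samples are spaced by at least 5 days. The exclusion of "Patients previously recruited to the study" and the first no-inflation reason both read as if there were one sampling occasion per patient. If that were so, participant and sample exclusion would coincide, and only the points on failed runs and on 11.1 would remain. Those passages should be reconciled with 7.4.

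**The precision targets are not fragile.** A reader might infer that any exclusion breaks the rare-pathogen target, because 4501 gives an expected nine cases. The figures do not support that: nine cases give 19.6 points, and the target survives about 4% loss. At 5% loss the miss is 0.1 point. The expected loss of 0.45 cases is small beside the chance variation of a count of nine (SD about 3).

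**Failures will not go unreported.** A reader might infer that the plan hides device failures. Section 11.2 commits to accounting for losses, so the exact criticism is that failures stay out of the estimates. Bedside failures may also be rescued by the central run, and rules for repeat runs may be in an SAP that is not shown.

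**The no-inflation reasons have some bearing.** A reader might call them irrelevant. However, the secondary analysis in section 5.1 uses cultures within 7 days, so attrition matters there, and drawing both samples at one event makes pairing likely. The reasons are incomplete.

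None of this rescues the wording of 11.3. The protocol does not leave the rule to the SAP; it fixes one that does not fit its own unit.

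**Conclusion.** The point holds as a mismatch of unit and scope in 11.3 and an incomplete justification in 11.1. Followed literally, the rule discards complete pairs, more often from patients with more samples, and keeps failed PCR runs out of the accuracy, time-to-result and cost estimates.

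Its size cannot be fixed from the protocol. At an assumed 5% failure rate the extra loss runs from nothing (one sample each) through 1.6 percentage points (6.6% against 5%) to 3.3 points (8.3% against 5%). Losses of that order take the rare-pathogen half-width just past 20 points but leave the overall target intact; the latter gives way only at about 14% loss. All of this assumes failures independent between samples.

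It would go too far to conclude that the primary sensitivity or specificity will be materially wrong. Selective loss of longer-stay patients follows from the rule, but its effect on accuracy cannot be quantified from the protocol. The correction is worth making because it is nearly free and should be settled before results are seen.

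**What to change.** 1. In 11.3, replace 'participant' with 'sample (PCR-culture pair)', and exclude a sample only from analyses that need the missing item. State whether a failed bedside run with a valid central result counts as absent, and for which analysis.
2. Report the number and rate of absent or failed PCR results, separately for point-of-care and central testing.
3. Add a sensitivity analysis. In culture-positive samples, count a failed run as a non-detection when estimating sensitivity. In culture-negative samples, do not credit a failed run as a true negative. Scoring every failure as not detected would raise specificity: with 95% among completed runs and 5% failures, 0.95 × 0.95 + 0.05 = 95.25%.
4. In 11.1, state that 3851 and 4501 are evaluable sample pairs, and restate the expected precision for a plausible range of non-evaluable samples, for example 5-15%: 2.84 to 3.01 points overall and 20.11 to 21.26 points for uncommon pathogens.

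Cost: wording in two sections, one extra table, and slightly less favourable stated precision. Section 9.1 lists the PCR result and completion time but no explicit item for a failed run. If the CRF does not capture this, one field is needed.
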